9.1 Discontinuation Criteria for Individual Patients

9.1.1 Patient Withdrawal

Patients may voluntarily withdraw consent to participate in the clinical study at any time and without giving any reason. Their withdrawal will not jeopardize their relationship with their healthcare providers or affect their future care. Patients may also choose to withdraw from study treatment, but agree to remain in the study for follow-up procedures.

9.1.2 Investigator Discontinuation of Patient

The investigator may exercise medical judgment to discontinue study treatment if clinically significant changes in clinical status or laboratory values are noted.

9.1.3 Criteria for Protocol-Defined Required Discontinuation of Treatment

The protocol requires discontinuation of study treatment for the following reasons:

1. Patient requests discontinuation.
2. Unacceptable toxicity that in the opinion of the investigator makes it unsafe to continue therapy.
3. Clinically significant progressive disease.

4. Investigator discretion.

9.1.4 Follow-Up at Treatment Discontinuation or Early Withdrawal

Patients who discontinue treatment for any reason should complete end-of-treatment procedures when possible. End of treatment procedures will include a physical examination, CBC with differential and platelets and a limited chemistry profile (total bilirubin, serum creatinine, SGPT or SGOT). A bone marrow aspiration may be recommended only if non-response or progressive disease cannot be unequivocally diagnosed from peripheral blood. Although treatment will be discontinued at that time, all patients who do not withdraw consent for follow-up, die, or become lost to follow-up, will remain on study for follow-up evaluations. Subject will be followed for toxicity for at least 30 days after the last protocol treatment. The 30-day follow-up visit will be scheduled as a clinic visits for clinical evaluation and physical examinations. If the patient cannot make it to the MDACC clinic for this visit, the required follow up treatment procedures may be done with a local physician and the records forwarded to MDACC. The research nurse will contact the patient by telephone and get a verbal assessment of the patient's condition. The phone conversation will then be documented in the patient's charts.

9.2 Study Stopping Rules

The principal investigator and MDACC IND office have the right to terminate this clinical study at any time. The principal investigator and MDACC IND office, as appropriate, will be involved in any decisions regarding terminating the study, temporarily suspending enrollment, or stopping ongoing treatment with study treatment.

Reasons for terminating the clinical study or a study site's participation include, but are not limited to, the following:

- The incidence or severity of an adverse reaction related to treatment in this study or other studies indicates a potential health hazard to patients
- Data recording is significantly inaccurate or incomplete
- Study site personnel are noncompliant with study procedures
- Pattern of noncompliance is observed

9.3 Protocol Violations and Deviations

Protocol violations are defined as significant departures from protocol-required processes or procedures that affect patient safety or benefit potential, or confound assessments of safety or clinical activity. A protocol deviation is a departure from the protocol that does not meet the above criteria. Protocol violations or deviations may be grouped into the following classes:

- Enrollment criteria
- Study activities (missed evaluations or visits) except for those allowed per protocol
- Noncompliance with dose or schedule, including dose calculation, administration, interruption, reduction, or delay; or discontinuation criteria
- Investigational product handling, including storage and accountability
- Informed consent and ethical issues

10 ADVERSE EVENT REPORTING

- 10.1** Adverse event is any untoward medical occurrence that may present during treatment with a pharmaceutical product but which does not necessarily have a causal relationship with this treatment.

Adverse drug reaction is a response to a drug which is noxious and unintended and which occurs at doses normally used in man for prophylaxis, diagnosis, or therapy of disease or for the modification of physiologic function.

Assessing causal connections between agents and disease is fundamental to the understanding of adverse drug reactions. In general, a drug may be considered a contributory cause of an adverse event if, had the drug not been administered, 1) the event would not have happened at all, 2) the event would have occurred later than it actually did, or 3) the event would have been less severe.

The Investigator or physician designee is responsible for verifying and providing source documentation for all adverse events and assigning the attribution for each event for all subjects enrolled on the trial.

- 10.2 Adverse Events (AEs) will be evaluated according to the latest CTC version 4 (Appendix C) and documented in medical record. Only unexpected AEs will be recorded in the Case Report Form (CRF). Expected events during leukemia therapy are:**

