 2. A letter to the local physician outlining the patient's participation in a clinical trial will request local physician agreement to supervise the patient's care (Appendix H)
 3. Protocol required evaluations outside MDACC will be documented by telephone, fax or e-mail. Fax and/or e-mail will be dated and signed by the MDACC physician, indicating that they have reviewed it. Changes in drug dose and/or schedule must be discussed with and approved by the MDACC physician investigator, or their representative prior to initiation, and will be documented in the patient record.
 4. A copy of the informed consent, protocol abstract, treatment schema and evaluation during treatment will be provided to the local physician.
 5. Documentation to be provided by the local physician will include progress notes, reports of protocol required laboratory and diagnostic studies and documentation of any hospitalizations.
 6. The home physician will be requested to report to the MDACC physician investigator all life threatening events within 24 hours of documented occurrence.
 7. All follow-up visits will be performed at MDACC. Patients will return to MDACC for physical examination at the start of each cycle i.e. approximately every 28 days (+/-7).
- 7.2.10 End of Treatment Visit to be completed 30 days (+/-7 days) after the last dose of study drug. Blood (about 2-3 teaspoons) will be drawn for CBC, platelet count, differential, creatinine, total bilirubin, ALT. No other procedures or labs will be needed.
- 7.2.11 Patients with an objective response at completion of active study treatment will be followed for survival at MD Anderson Cancer Center (MDACC) for up to 90 days after completion of active treatment and while still on study. If the patient is unable to return to MDACC the follow-up visits may be conducted via telephone.

Data regarding adverse events will be collected during the study. Please see **Appendix D** regarding data capturing of adverse events and adverse events source documentation. Protocol specific data will be entered into PDMS/CORE. PDMS/CORE will be used as the electronic case report form for this protocol. Only unexpected AEs will be recorded in the Case Report Form (CRF). The Principal Investigator will sign and date the AE log per each

patient at the completion of each course. Following signature, the AE log will be used as source documentation for the adverse events for attribution.

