10.2.6 Myelosuppression related events (due to disease or leukemia therapy)

10.2.6.1 febrile or infection episodes not requiring management in the intensive care unit

10.2.6.2 epistaxis or bleeding except for catastrophic CNS or pulmonary hemorrhage

10.2.6.3 anemia, neutropenia, lymphopenia, thrombocytopenia, leukopenia

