10.2.7 Disease related events

10.2.7.1 symptoms associated with anemia

10.2.7.1.1 fatigue

10.2.7.1.2 weakness

10.2.7.1.3 shortness of breath

10.2.7.2 electrolyte abnormalities (sodium, potassium, bicarbonate, CO₂, magnesium)

10.2.7.3 chemistry abnormalities (LDH, phosphorus, calcium, BUN, protein, albumin, uric acid, alkaline phosphatase, glucose)

10.2.7.4 coagulation abnormalities

10.2.7.5 disease specific therapy (induction, maintenance, salvage, or stem cell therapy)

10.2.7.6 alopecia

10.2.7.7 bone, joint, or muscle pain

10.2.7.8 liver function test abnormalities associated with infection or disease progression

10.2.7.9 disease progression

10.2.7.10 abnormal hematologic values

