10.2.9 Hospitalization for the management of any of the above expected events

10.3 Abnormal hematologic values will not be recorded on the case report form. For abnormal chemical values, the apogee or nadir (whichever is appropriate) will be reported per course on the case report form.

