All patients who received any dose of the study agent will be included in the analysis for efficacy and safety. Demographic/clinical characteristics (including duration of response) and safety data of the patients will be summarized using descriptive statistics such as mean, standard deviation, median and range. For the primary efficacy analysis, we will estimate the ORR for the combination treatment, along with the 95% confidence interval. Patients who drop out of the study before completing all the cycles will be treated as “failures” for the primary analysis. ORR during the study period will also be presented with the 95% confidence interval. The association between ORR and patient’s clinical characteristics will be examined by Wilcoxon’s rank sum test or Fisher’s exact test, as appropriate. Toxicity type, severity and attribution will be summarized for each patient using frequency tables.

The distribution of time-to-event endpoints (DFS and OS) including overall survival and progression free survival will be estimated using the method of Kaplan and Meier. Comparisons of time-to-event endpoints by important subgroups will be made using the log-rank tests. Paired t-tests will be used to determine the immunological and molecular changes in the peripheral blood and bone marrow from baseline to the time of response, and to the time of disease progression. Correlation analysis (such as logistic regression analysis) will be conducted to determine the relationship between induction of hypomethylation / DNA damage and clinical response.

Statistical analysis of biomarker data: Descriptive statistics including plots, mean, median and standard deviations will be used to summarize data. For continuous outcomes, t-test and ANOVA will be used to compare outcome measures across patient characteristics. Dunnett’s and Tukey’s test that properly adjust for multiplicity in multiple tests will be implemented. Pair-wise comparisons will be performed using pre- and post-therapy samples from each patient . The chi-square test or Fisher’s exact test will be used to test the association between two categorical variables such as disease state and performance status. Both univariate and multivariate logistic regressions will be performed to model prognostic factors.

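### The CRF leaves out every expected adverse event whatever its grade or attribution, and no data source is named for the toxicity stopping rule or the safety tables

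*Combined protocol and SAP*

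**What the plan says.** The recording rule appears twice, in section 10.2 and in the data paragraph that follows item 7.2.11: "Only unexpected AEs will be recorded in the Case Report Form (CRF"). That paragraph also identifies the database: "PDMS/CORE will be used as the electronic case report form for this protocol". No other study database is named.

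The expected list (10.2.6 to 10.2.9) carries no grade threshold. Its first group is headed "Myelosuppression related events (due to disease or leukemia therapy") and covers the cytopenias, most bleeding, and "febrile or infection episodes not requiring management in the intensive care unit". The disease-related group includes "bone, joint, or muscle pain". The list closes with "Hospitalization for the management of any of the above expected events". Section 10.3 adds "Abnormal hematologic values will not be recorded on the case report form", although the worst chemistry value per course is recorded.

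On the statistical side, section 11.2 treats a drug-related grade 3/4 toxicity rate above 30% as unacceptable. Table 4 gives the number of affected patients at which accrual stops. No category of event is excluded. The safety analysis is described as "Toxicity type, severity and attribution will be summarized for each patient using frequency tables". Safety of the combination is a secondary objective (section 1.2).

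**The concern.** The stopping rule and the safety tables are defined by grade and attribution, whereas CRF entry is decided by expectedness. These criteria differ. A grade 4 neutropenia attributed to 5-azacytidine is a drug-related grade 3/4 event on the wording of section 11.2, yet it stays out of the CRF. The same holds for a drug-attributed grade 3 infection managed outside intensive care.

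The plan does not say which record supplies the Table 4 count. If the study database is used, as would be natural for both interim monitoring and the final tables, the observed toxicity rate can only be too low. The rule would then be less likely to stop a regimen whose true rate exceeds the 30% limit, and the reported safety profile would omit treatment-caused events. If another record is used, two people monitoring the same patients need instructions that the protocol does not give.

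**Working it through.** **1. Reproducing the plan's own figure.** Inputs from section 11.2: looks after every 5 patients from 5 to 35, maximum 40; Table 4 stops at 4/5, 6/10, 8/15, 10/20, 12/25, 14/30 and 16/35 or more. Let S_tox(p) be the probability of never reaching the Table 4 boundary when each patient independently has a counted toxicity with probability p. It comes from an exact binomial recursion over the seven looks. S_fut(r) is the same for futility at response rate r. With toxicity and response independent,

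P(stop early) = 1 − S_tox(p) × S_fut(r).

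At p = 0.50, 1 − S_tox = 0.8345. At r = 0.30, 1 − S_fut = 0.0323, using a futility boundary one response below printed Table 5 (0 at 10–15 patients, 1 or fewer at 20–25, 2 or fewer at 30–35). Then 1 − 0.1655 × 0.9677 = 0.8398, as printed in Table 6. With Table 5 as printed the cell is 0.8605. That mismatch is a separate matter and does not affect the toxicity part used below.

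**2. Effect of a CRF-only count.** Table 4 counts patients, so the relevant quantity is m, the share of patients with a drug-related grade 3/4 toxicity who have none recorded in the CRF. The documents give no value, so m is an assumption shown over a range. The counted rate is p × (1 − m). For a true rate of 50%:

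| m (assumed) | counted rate | Table 4 stops | toxicity or futility stops, ORR 30% |
|---|---|---|---|
| 0 | 0.50 | 0.8345 | 0.8398 |
| 0.10 | 0.45 | 0.6654 | 0.6762 |
| 0.20 | 0.40 | 0.4566 | 0.4741 |
| 0.40 | 0.30 | 0.1231 | 0.1514 |
| 0.60 | 0.20 | 0.0149 | 0.0466 |

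The last column uses the futility boundary that reproduces Table 6.

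**3. Events versus patients.** A share e of missed events equals m only if each affected patient has one such event. With two independent events per affected patient, m = e². Missing 20%, 40% or 60% of events then loses 4%, 16% or 36% of patients. The counted rates are 0.48, 0.42 and 0.32, and Table 4 stops with probability 0.77, 0.54 and 0.17.

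**4. Is overlap plausible?** Section 2.4 describes related events in the blinded maintenance trial: nine Grade 3 reports and one Grade 4, ten in all. Six match terms on this protocol's expected list (neutropenia 4, thrombocytopenia 1, myalgia 1), so 4/10 would be recorded. Five of the six are cytopenias. This shows only that overlap occurs. Those patients received lirilumab or placebo without 5-azacytidine, and ten reports cannot fix m for this trial.

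**The case against.** A reader might infer that the stopping rule and the safety objective do run on an undercount. The documents do not establish that, because section 11.2 names no source and other records exist. Section 10.1 requires source documentation and attribution for all adverse events. Section 10.2 has them graded and documented in the medical record. The investigator signs an AE log each course. All SAEs, expected or not, go to the IND Office (10.4). At a single centre, counting from these records is feasible. Appendix D, which governs adverse event capture, was not available. This objection stands, and it makes the point conditional. It does not remove it: SAE reports miss non-serious grade 3/4 events, the protocol does not say whether the AE log includes expected events, and nothing directs the Table 4 count to any of these records.

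The expected list can also be over-read. Fatigue, weakness and shortness of breath appear only as symptoms of anemia. Musculoskeletal pain sits under disease-related events, and an event judged due to disease would not count in Table 4 anyway. Sciatica is not listed. The 10% asthenia figure from the maintenance trial covers all grades and says nothing about a grade 3/4 rule. Colitis and pneumonitis are not listed and would be recorded. The lead-in DLT definition is non-hematologic, so the dose decision is less exposed.

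Finally, the rule may have been meant to leave out expected myelosuppression: the DLT definition does so, and section 5.3.1 plans no adjustment for it in the first 4 cycles. If so, much of the apparent loss is intended. But section 11.2 does not say this, and the monitored event is then undefined. Entering all drug-related cytopenias without settling the question could make Table 4 stop for events that the design did not mean to count.

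**Conclusion.** The point holds in conditional form. The recording rule is explicit and conflicts with a stopping rule and safety tables defined on drug-related events without exclusion. If the CRF is the source, the toxicity count and the safety summary are biased downward. At a true 50% rate, losing even 10% of affected patients costs about 17 percentage points of stopping probability (0.8345 − 0.6654 = 0.169), and losing 40% leaves the rule with a 0.12 chance of stopping. These sizes rest on an assumed share of missed patients, independence between patients, and Table 4 as printed. They are upper illustrations if the assumed share is of events and patients typically have more than one. Confidence is moderate: the AE log and medical record may already supply complete counts, and the text of Appendix D could settle the source.

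**What to change.** Three changes to sections 7.2, 10.2 and 11.2:

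1. Record in the CRF every grade 3 or higher adverse event, and every adverse event attributed to either study drug, with grade and attribution, whether or not it is on the expected list. Grade 1–2 expected events attributed to neither drug can stay out.
2. Name that record as the source for the Table 4 counts and the safety tables.
3. State in section 11.2 whether expected myelosuppression counts toward the monitored toxicity, and reconcile that statement with the DLT definition (5.2.1.3), the hematologic adjustment text (5.3.1), the myelosuppression list (10.2.6) and the 30% limit. Which way to settle it is for the sponsor and the investigator.

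The cost is modest extra data entry for at most about 58 patients (24 in the lead-in plus 34 further patients). Sections 10.1 and 10.2 already require grading and attribution, so no new assessment is needed.

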10.2.6 Myelosuppression related events (due to disease or leukemia therapy)

10.2.6.1 febrile or infection episodes not requiring management in the intensive care unit

10.2.6.2 epistaxis or bleeding except for catastrophic CNS or pulmonary hemorrhage

10.2.6.3 anemia, neutropenia, lymphopenia, thrombocytopenia, leukopenia

10.2.7 Disease related events

10.2.7.1 symptoms associated with anemia

10.2.7.1.1 fatigue

10.2.7.1.2 weakness

10.2.7.1.3 shortness of breath

10.2.7.2 electrolyte abnormalities (sodium, potassium, bicarbonate, CO₂, magnesium)

10.2.7.3 chemistry abnormalities (LDH, phosphorus, calcium, BUN, protein, albumin, uric acid, alkaline phosphatase, glucose)

10.2.7.4 coagulation abnormalities

10.2.7.5 disease specific therapy (induction, maintenance, salvage, or stem cell therapy)

10.2.7.6 alopecia

10.2.7.7 bone, joint, or muscle pain

10.2.7.8 liver function test abnormalities associated with infection or disease progression

10.2.7.9 disease progression

10.2.7.10 abnormal hematologic values

10.2.8 General therapy related events

10.2.8.1 catheter related events

10.2.8.2 renal failure related to tumor lysis syndrome or antibiotic/antifungal therapy

10.2.8.3 rash related to antibiotic use

10.2.9 Hospitalization for the management of any of the above expected events

10.3 Abnormal hematologic values will not be recorded on the case report form. For abnormal chemical values, the apogee or nadir (whichever is appropriate) will be reported per course on the case report form.

10.4 Serious Adverse Event Reporting (SAE)

An adverse event or suspected adverse reaction is considered “serious” if, in the view of either the investigator or the sponsor, it results in any of the following outcomes:

- Death
- A life-threatening adverse drug experience – any adverse experience that places the patient, in the view of the initial reporter, at immediate risk of death from the adverse experience as it occurred. It does not include an adverse experience that, had it occurred in a more severe form, might have caused death.
- Inpatient hospitalization or prolongation of existing hospitalization

- A persistent or significant incapacity or substantial disruption of the ability to conduct normal life functions.
- A congenital anomaly/birth defect.

Important medical events that may not result in death, be life-threatening, or require hospitalization may be considered a serious adverse drug experience when, based upon appropriate medical judgment, they may jeopardize the patient or subject and may require medical or surgical intervention to prevent one of the outcomes listed in this definition. Examples of such medical events include allergic bronchospasm requiring intensive treatment in an emergency room or at home, blood dyscrasias or convulsions that do not result in inpatient hospitalization, or the development of drug dependency or drug abuse (21 CFR 312.32).

- Important medical events as defined above, may also be considered serious adverse events. Any important medical event can and should be reported as an SAE if deemed appropriate by the Principal Investigator or the IND Sponsor, IND Office.
- All events occurring during the conduct of a protocol and meeting the definition of a SAE must be reported to the IRB in accordance with the timeframes and procedures outlined in “The University of Texas M. D. Anderson Cancer Center Institutional Review Board Policy for Investigators on Reporting Unanticipated Adverse Events for Drugs and Devices”. Unless stated otherwise in the protocol, all SAEs, expected or unexpected, must be reported to the IND Office, regardless of attribution (within 5 working days of knowledge of the event).
- **All life-threatening or fatal events**, that are unexpected, and related to the study drug, must have a written report submitted within **24 hours** (next working day) of knowledge of the event to the Safety Project Manager in the IND Office.
- Unless otherwise noted, the electronic SAE application (eSAE) will be utilized for safety reporting to the IND Office and MDACC IRB.
- Serious adverse events will be captured from the time of the first protocol-specific intervention, until 30 days after the last dose of drug, unless the participant withdraws consent. Serious adverse events must be followed until clinical recovery is complete and laboratory tests have returned to baseline, progression of the event has stabilized, or there has been acceptable resolution of the event.
- Additionally, any serious adverse events that occur after the 30 day time period that are related to the study treatment must be reported to the IND Office. This may include the development of a secondary malignancy.

Reporting to FDA:

- Serious adverse events will be forwarded to FDA by the IND Sponsor (Safety Project Manager IND Office) according to 21 CFR 312.32.

It is the responsibility of the PI and the research team to ensure serious adverse events are reported according to the Code of Federal Regulations, Good Clinical Practices, the protocol guidelines, the sponsor's guidelines, and Institutional Review Board policy

10.5 Serious Adverse event Reporting to Bristol-Myers Squibb Inc.

All Serious Adverse Events must be reported to BMS Worldwide Safety

- All SAEs, whether related or unrelated to lirilumab and all pregnancies must be reported to BMS (by the investigator or designee) within 24 hours.
- All SAEs should be reported via confirmed facsimile (fax) transmission.
- **SAE [contact]

